5.2.2 Post-NAT Evaluation

For patients undergoing NAT, repeat evaluation with imaging studies will be performed at the conclusion of NAT treatment,. Imaging will include dedicated pre-surgical breast MRI in both prone and supine positions, as well as ultrasound and mammography as deemed necessary by the treatment team. Imaging protocols utilized for post-NAT evaluation will be per institutional standards and will be consistent with those utilized for pre-NAT evaluation.

These imaging studies will then be reviewed by the treating radiologist and surgeon, and determination will be made if a radiographic complete response (rCR) has occurred. Quality of the supine MRI sequence will be determined by the attending radiologists, and at this time if the quality is deemed unacceptable for interpretation, the image will not be utilized in residual tumor calculations. If rCR has not occurred, estimated sizes and volumes of the remnant tumor will be made using each imaging modality by the treating radiologist and recorded in standard format. If additional disease is uncovered at this time, it will also be recorded. Using the information obtained from the totality of imaging studies, the surgeon will determine whether or not the patient is eligible to proceed with BCT or mastectomy.

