Limitations of other modalities are numerous. For example, NAT can induce unpredictable fibrous changes that can reduce the reliability of clinical examination. Certain breast cancer subtypes, such as lobular carcinoma for example, are difficult to visualize mammographically and can increase in firmness after NAT, causing an initially occult lesion to become more clinically palpable with treatment[30]. Assessment of tumor size on exam and with mammography can be undermined by the infiltrative nature of locally advanced breast cancers, especially in the setting of dense breast tissue [25, 26, 31]. Suspicious microcalcifications initially noted on mammogram may persist, become coarser, or occasionally increase on mammograms after NAT. Peintinger et al demonstrated that a combination of mammogram and ultrasound could provide moderate agreement in predicting residual tumor size after NAT; however, the correlation and agreement with pathologic residual tumor size was underestimated for lobular carcinoma and overestimated for poorly differentiated tumors [32]. Yeh et al also demonstrated similar findings when comparing agreement regarding the rate of response between clinical examination, mammography, sonography, and MRI with pathology as the reference standard, with agreement rates of 19%, 26%, 35%, and 71%, respectively [26]. Although MRI was noted to be the superior modality in this study, it was not without its own limitations; MRI was felt to both underestimate and overestimate residual tumor measurements, leaving clinicians with an ongoing need for an improved way to monitor the response to and the disease remaining after NAT regimens.

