For patients who received NAT, post-NAT pre-operative breast MRI with supine sequence will be obtained. If tumor was visible pre-NAT on the other imaging modalities such as mammogram, 2D and/or 3D ultrasound they will also be performed at post-NAT. These images will be used to determine if preoperative lesion localization is necessary using either radioactive seed or wire placement; if required, these images will be utilized by the breast imaging service preoperatively for lesion localization procedure per standard practice and the radiologist will be surveyed post-localization regarding usefulness of supine MRI for lesion localization procedure. Supine MRI will be provided in addition to standard imaging modality images for patients ultimately eligible for breast conserving surgery for preoperative surgical planning and for intraoperative tumor resection.

Patients enrolled to participate in this study will receive standard of care with breast conserving therapy or mastectomy for local therapy. Detailed risks and benefits of participating in the study will be reviewed with patients prior to obtaining consent, and all questions will be answered. After general endotracheal anesthesia is induced, the standard operation will be performed by a breast surgical oncologist, including a lumpectomy or mastectomy, with or without sentinel node biopsy and/or possible axillary dissection. The surgical specimen will be sent for standard histopathology. Final specimens will include the original lumpectomy specimen, any nodal tissue (sentinel node(s) versus axillary dissection components if nodal procedure was performed), and shave margins/targeted re-excisions. These samples will be sent for analysis by pathology.

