9.2 Sample Size, Accrual Rate and Study Duration

For the primary outcome, with 73 eligible patients we will have 90% power to detect a correlation coefficient between pre-surgical prone or supine MRI and tumor size of 0.85 from 0.70 with a two-sided one sample z-test at $\alpha=0.05$ level.

With 73 eligible patients, we will also have more than 80% power to detect a difference in correlation from 0.85 between the supine MRI and the pathology tumor size and 0.70 between the standard imaging and the pathology tumor size with a two-sided two sample z-test at $\alpha=0.05$ level, assuming the correlation between the supine MRI and the standard imaging is 0.70.

Assuming the dropout rate will be 10%, we will plan to accrue a total of 80 patients. With an anticipated enrollment of 5 patients per month, accrual should be completed in approximately 16 months.

The below table “Accrual Targets” reflects the accrual targets anticipated for this study. As noted in detail in Section 3.3, men are not likely candidates for breast conserving surgery, and are not eligible for this trial. Approximately 10% of the target enrollment will be Hispanic or African American.

Accrual Targets					
Ethnic Category	Sex/Gender				
	Females	+	Males	=	Total
Hispanic or Latino	8	+	0	=	8
Not Hispanic or Latino	72	+	0	=	72
Ethnic Category: Total of all subjects	80 (A1)	+	0 (B1)	=	80 (C1)
Racial Category					
American Indian or Alaskan Native	1	+	0	=	1
Asian	4	+	0	=	4
Black or African American	12	+	0	=	12
Native Hawaiian or other Pacific Islander	0	+	0	=	
White	63	+	0	=	63
Racial Category: Total of all subjects	80 (A2)	+	0 (B2)	=	80 (C2)

(A1 = A2)

(B1 = B2)

(C1 = C2)

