9.5 Analysis of Primary Endpoints

There are three primary objectives of this study, each with unique endpoints.

The first is to evaluate the correlation between prone breast MRI and pathologic measurement in estimating tumor size, and the correlation between supine breast MRI and pathologic results. A 95% confidence interval will also be calculated for each correlation coefficient. One sample z-test will be conducted to compare whether these correlation coefficients are different from 0.6.

The second is to compare the correlation between supine breast MRI and pathologic measurement for estimation of tumor size, and the correlation between existing breast imaging modalities and pathologic tumor size. Similarly, correlation coefficient will be calculated between supine MRI and the pathologic results and between existing breast imaging modalities and the pathologic tumor size. Two-sample z-test for comparing correlated correlation coefficients will be conducted to compare whether these two correlation coefficients are equal.

The third is to characterize the changes occurring in breast tumor-associated properties/ dimensions between the prone and supine imaging position for all patients with pre-surgical MRIs. We will also determine the correlation of tumor location and geometry on pre-NAT and post-NAT (pre-surgical) supine MRI with prone MRI among the subgroup of patients with pre and post NAT imaging. As described in Section 2.1, in our prior work comparing prone to supine MRI, we utilized image processing software that enabled us to generate tumor models and specifically calculate differences in the metrics computed from the segmented tumor label maps on supine and prone MRI. As a first order statistics, we plan to examine differences in the shape

and size of the tumor on supine and prone MRI. Further, we hope to correlate these difference metrics with variables including but not limited to breast size (measured on the axial slice through the nipple) and location (inner/outer, upper/lower). Correlation coefficients will be calculated for parameters related to tumor shape and size between supine and prone MRI, and one sample t-test (or non-parametric Wilcoxon test) will be used to test whether the difference in shape and size parameters between these two measurements are significantly different from 0. A regression model will be used to check whether these differences are correlated to breast size and location, age and other clinical characteristics.

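### Section 9.5 tests the MRI–pathology correlations against 0.6, while section 9.2 sizes the same primary test against 0.70; the size to enter for a complete response should also be written down

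*Combined protocol and SAP*

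**What the plan says.** **The primary test.** Section 9.5 covers the correlation of prone MRI size, and of supine MRI size, with pathologic size. It says: "One sample z-test will be conducted to compare whether these correlation coefficients are different from 0.6". It adds: "A 95% confidence interval will also be calculated for each correlation coefficient". Section 9.2 claims 90% power with 73 eligible patients at the two-sided 0.05 level for a correlation between "prone or supine MRI and tumor size of 0.85 from 0.70 with a two-sided one sample z-test". Section 2.1 reports that prone MRI after neoadjuvant therapy (NAT) correlates with pathology at about 0.7; the four cited studies give 0.71, 0.75, 0.72 and 0.75. No section gives a reason for 0.6.

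**Complete response.** Section 5.2.2 has the radiologist and surgeon decide whether a radiographic complete response (rCR) has occurred, and continues: "If rCR has not occurred, estimated sizes and volumes of the remnant tumor will be made using each imaging modality by the treating radiologist". It attaches no size to the other branch. For a supine sequence of unacceptable quality it says "the image will not be utilized in residual tumor calculations". Ultrasound and mammography after NAT are conditional: section 5.2.2 includes them "as well as ultrasound and mammography as deemed necessary by the treatment team", and section 5.1 repeats them "If tumor was visible pre-NAT on the other imaging modalities". Section 9.7 excludes patients with MRI-related problems and patients without surgery at the institution. Neither exclusion concerns complete response.

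**The concern.** Sections 9.2 and 9.5 describe one test of one primary objective and give it two null values. The null decides whether the result is called significant, so the plan can produce two opposite conclusions from the same data. It also means that the stated sample size and power describe a test other than the one section 9.5 would run.

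The choice bears on interpretation as well. The cited studies put prone MRI at 0.71 to 0.75. A test against 0.6 asks whether MRI does better than a value below that benchmark; a test against 0.70 asks roughly whether it does better than the benchmark. Only the second matches the aim implied by the 0.85 alternative.

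The unwritten size for a complete response is a lesser matter. It affects NAT patients only, but it settles what numbers they contribute to objectives 1 and 2, and it is better settled before the data are seen.

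**Working it through.** **Inputs.** From section 9.2: n = 73, null 0.70, alternative 0.85, two-sided alpha 0.05, power 90%. From section 9.5: null 0.6. From section 2.1: 0.71, 0.72, 0.75. Assumption: the one-sample z-test is the Fisher z-test. The plan does not name the transformation, but step 1 shows that it reproduces the plan's figures.

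Transforms: atanh(0.85) = 1.2562, atanh(0.70) = 0.8673, atanh(0.6) = 0.6931; √(73 − 3) = 8.3666.

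**1. The plan's own figure (null 0.70).**
Power = Φ[(1.2562 − 0.8673) × 8.3666 − 1.960] = Φ(1.293) = 90.2%.
n for 90% = [(1.960 + 1.2816) / 0.3889]² + 3 = 72.5, rounded up to 73.
Both agree with section 9.2. A one-sided test would need 60, so the two-sided version is the one used.

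**2. The same formula with the null of section 9.5 (0.6).**
Power = Φ[(1.2562 − 0.6931) × 8.3666 − 1.960] = Φ(2.75) = 99.7%.
n for 90% = [3.2415 / 0.5630]² + 3 = 36.1, rounded up to 37.

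**3. Cut-offs for the observed r at n = 73:** tanh[atanh(null) ± 1.960/8.3666], where 1.960/8.3666 = 0.2343.
Null 0.6: tanh(0.4589) = 0.429 and tanh(0.9274) = 0.729.
Null 0.70: tanh(0.6330) = 0.560 and tanh(1.1016) = 0.801.

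| Observed r | Against 0.6 | Against 0.70 |
|---|---|---|
| below 0.429 | significantly lower | significantly lower |
| 0.429 to 0.560 | not significant | significantly lower |
| 0.560 to 0.729 | not significant | not significant |
| 0.729 to 0.801 | significantly higher | not significant |
| above 0.801 | significantly higher | significantly higher |

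**4. Chance of a significantly higher result if MRI performs as in the cited studies (n = 73).** For true r = 0.71 against 0.6: Φ[(0.8872 − 0.6931) × 8.3666 − 1.960] = Φ(−0.337) = 37%. The others follow in the same way.

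| True r | Null 0.6 | Null 0.70 |
|---|---|---|
| 0.71 | 37% | 4% |
| 0.72 | 43% | 5% |
| 0.75 | 65% | 14% |

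**5. Entering zeros for complete response: direction only.** The inputs here are assumptions, since the documents give no NAT share, no rCR rate and no size distribution. Take mean size 2, SD 1 and r = 0.70 among tumors seen both on imaging and at pathology.
- A share f of patients is zero on both measures, with no disagreement: r = [(1 − f)(0.70) + 4f(1 − f)] / [(1 − f) + 4f(1 − f)]. For f = 10%, this is 0.99/1.26 = 0.79; for 20%, 1.20/1.44 = 0.83; for 30%, 1.33/1.54 = 0.86.
- A further 5% are zero on imaging only and 5% zero at pathology only. Let p be the share positive on both and q the share positive on one given measure. Then r = [4.7p − 4q²] / [q + 4q(1 − q)]. For f = 10% (p = 0.80, q = 0.85) this is 0.87/1.36 = 0.64; for 20%, 1.04/1.50 = 0.69; for 30%, 1.13/1.56 = 0.72.

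So the coefficient can land above or below the 0.70 assumed for visible tumors, depending on how often imaging and pathology disagree about complete response.

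**The case against.** **On the null.** Section 9.5 also requires a 95% confidence interval for each correlation, so a reader can check either value. Rejecting 0.6 when the true correlation is 0.71 to 0.75 is a correct rejection, not a false positive. And the 0.70 benchmark comes from post-NAT patients, whereas this trial also enrolls patients going straight to surgery. All three points stand. They soften the consequence without removing the contradiction: the planned test still has two nulls, and only 0.70 has support in the documents. It would be too strong to say that the 0.6 test inflates type I error or that the trial is underpowered. A rejection of 0.6 simply would not show improvement over the benchmark, and power against 0.6 is higher, not lower.

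**On complete response.** A reader might infer that rCR patients will drop out of the primary analysis, biasing the correlation and costing power. The documents do not support that. Section 5.2.2 does not say that sizes are recorded only when rCR is absent. Section 1.1 compares the size from each modality with pathology, and section 9.7 excludes no complete responders. Zero is therefore the more natural reading, and for pathology it is close to definitional. Any figure for patients lost would need the less natural reading plus NAT, response and imaging-clearance rates that the plan does not give. Section 2.1 says of an earlier study that "MRI was felt to both underestimate and overestimate residual tumor measurements", so disagreement in both directions is plausible and the net effect cannot be signed.

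**Conclusion.** The contradiction between sections 9.2 and 9.5 is real and rests on current text. It concerns primary objective 1 only; objective 2 compares two correlations with each other and has no fixed null. Its size needs no clinical assumption, only Fisher z and 73 evaluable patients: opposite verdicts for an observed r of about 0.73 to 0.80 and of about 0.43 to 0.56, and a required sample of 37 rather than 73 for the test as section 9.5 states it. With a different evaluable number the cut-offs would move, but the conflict would remain.

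The missing size for rCR and for a pathological complete response (pCR) is a clarification, not an error by itself. A reader might also infer that skewed tumor sizes invalidate the z-tests. The documents give no size distribution, so that is not claimed here.

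**What to change.** **Main change.** In section 9.5, replace 0.6 by 0.70, so that the analysis is the one section 9.2 sizes. The cost is a harder test: power for 0.85 is 90% instead of 99.7%. The report should say that the benchmark is post-NAT only.

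**Clarification.** State before analysis, in sections 5.2.2 and 9.5, that:
- a modality that was performed and shows no residual tumor is recorded as size 0;
- a modality not performed, or a supine sequence judged unreadable, is recorded as missing, so that a blank cannot mean both things;
- pCR is recorded as pathology size 0;
- a sensitivity analysis is restricted to patients with tumor seen both on imaging and at pathology.

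This costs protocol wording and one extra analysis. It has a downside: the documents do not show how the cited studies coded complete responses, so a coefficient that includes zeros may not be like for like with 0.70. As step 5 of the working shows, concordant zeros alone can raise r without any better sizing of visible tumors. The sensitivity analysis is there to show this.

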5.2.3 Surgery

Surgery will be either BCT or mastectomy (with appropriate nodal intervention including sentinel lymph node biopsy and/or axillary dissection), as deemed appropriate by the treating surgeon and according to current guidelines. Informed consent as per institutional standards will be obtained from the patient prior to surgery and all risks and benefits of surgical intervention and alternative options (no surgery) will be reviewed with the patient. When BCT is performed, standard cavity shave margins will be taken (as per institutional guidelines). At the conclusion of the operation, the surgical specimen will be sent for histopathology. Following completion of each BCT operation, the attending surgeon will be asked to complete a brief survey to assess their perceived usefulness of the supine MRI data in surgical planning/lesion localization.

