A total of 74 patients will be recruited to participate in this study. Enrolled patients will undergo upfront surgery or receive a NAT regimen at the discretion of the treatment team. All patients will have their breast tumor evaluated with standard imaging to include mammography, 2D and/or 3D, ultrasound, prone contrast-enhanced MRI and investigational supine contrast-enhanced MRI sequence pre-surgery. For patients planning for NAT, we will also attempt to obtain a prone contrast-enhanced MRI and investigational supine contrast-enhanced MRI sequence pre-NAT; however if a patient presents with an outside pre NAT MRI this will not be repeated. The tumor's position on all imaging modalities will be registered, and tumor location between supine and prone MRI sequences will be determined. Investigational supine MRI images will be provided to radiologists and surgeons for purposes of performing additional imaging interventions, if they are deemed necessary by the treatment team, and for surgical

planning. Estimates of tumor size pre-operatively as identified by each imaging modality will be compared to final pathology, allowing the correlation of each imaging modality for estimating residual tumor size with the gold standard method (pathology).

For patients undergoing BCT, the prone and supine MRI images will be registered in the image-processing software, 3D Slicer, and the segmented tumor models will be overlaid on the images. Screenshots showing the displacement of the tumor from the prone to the supine images will be provided to the surgeon to plan the tumor resection. Following completion of the operation a survey of the breast surgeon will be administered to determine their perceived usefulness of the supine imaging for surgical planning. Volume of excised tissue, rates of positive margins, and the need for reoperation, will be recorded, and these measures (using supine MRI imaging) will be compared to historical data to determine the impact of supine MRI imaging on surgical outcomes.

Patients requiring postoperative radiation therapy will be referred to radiation oncology post-operatively. Supine MRI images obtained prior to surgery will be provided to the radiation oncologists for breast treatment planning. A survey will then be administered to the attending treating radiation oncologist to assess the usefulness of supine MRI for treatment planning.

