7. STUDY CALENDAR

Assessment	Prior to upfront surgery or NAT treatment (within 3 months of registration)	Post-NAT Evaluation	Surgery	Post-operatively (within six weeks after surgery)
History and Breast Exam	X	X		X
Vital Signs	X			X
Conventional Mammogram with or without US	X	X		
Staging biopsy	X			
Informed Consent	X			
Prone MRI	X	X		
Supine MRI	X	X		
Second look Ultrasound / Mammography with/without biopsy*	X*			
Radiologist Surveys	X‡	X‡	X‡	
Surgery			X	
Surgeon Surveys				X
Pathology Review				X
Radiation Oncologist Survey				X†

*Second look ultrasound and/or biopsy will only be performed if deemed necessary by the treating team in scenarios in cases in which additional lesions are newly identified during MRI evaluation (this is an ‘optional’ and not ‘mandatory’ portion of the study)

‡ Radiologist surveys will be completed after second-look US performance (pre/post NAT) and/or at time of breast biopsies (pre/post NAT) and/or at time of lesion localization (day of surgery) when supine MRI information is used.

† Only in cases of patients who are referred for postoperative radiation therapy and have a treatment plan made by DFCI radiation oncologists.

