8.1 Data Reporting

8.1.1 Method

The trial is collecting limited data variables. The study team will collect, manage, and perform quality checks on the data for this study. The study will utilize a case report form collected after patients complete all study procedures and up to 30 days after their study completion. Surveys from providers will be collected at the completion of a patient's on study procedures. Data will be collected and shared with an outside collaborator for analysis. The data will not be identifiable.

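### The surgeon survey has no fixed timing relative to final pathology, so surgeons may rate supine MRI for planning after they know the margin result

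*Combined protocol and SAP*

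**What the plan says.** Three places describe what triggers the surgeon survey. Section 1.1: "Following completion of the operation a survey of the breast surgeon will be administered to determine their perceived usefulness". Section 5.2.3: "Following completion of each BCT operation, the attending surgeon will be asked to complete a brief survey". The question put to the surgeon is how much supine MRI helped with planning and with finding the lesion. Section 5.1 repeats the Section 5.2.3 sentence. All three place the survey after the operation, and none sets a time limit or mentions pathology as a cut-off.

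The study calendar (Section 7) is the only place that gives a window. The row "Surgeon Surveys" has one mark, in the column headed "Post-operatively (within six weeks after surgery". The row "Pathology Review" also has one mark, in that same column. The calendar does not say which comes first.

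Sections 5.1 and 5.2.4 say that positive margins on final pathology lead to further surgery where resection is possible, and that re-excision for close margins is left to the treating surgeon. Section 9.6 analyses the survey with a frequency table.

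**The concern.** Secondary objective 2 asks how useful surgeons found supine MRI for planning the resection. That judgement is best captured before the result of the resection is known. Once the surgeon has read the margin report, the answer can become partly a judgement of how the case turned out: more generous after clear margins, harsher after positive ones.

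Secondary objective 3 already measures margins and re-excision directly. If ratings under objective 2 are coloured by the same result, the two objectives are no longer separate pieces of evidence about supine MRI. The study has no concurrent control arm, and the planned table is not split by survey timing or margin status, so the timing of the survey is the main safeguard available. Section 1.1 names clinician surveys as one of the two kinds of measure for the study's hypotheses, so the endpoint is not incidental.

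**Working it through.** The plan gives no figure to reproduce here. The check sets the relevant places side by side.

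1. **Is there a deadline in the text?** Sections 1.1, 5.1 and 5.2.3 give a starting point (the operation is finished) and no end point.

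2. **Does the calendar supply one?** Yes, six weeks after surgery. In the surgeon-survey row the Surgery column is blank. The column as a whole is not: it carries marks for surgery itself and for the radiologist surveys.

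3. **Can the margin result arrive inside that window?** Pathology review has its only mark in the same post-operative column. The calendar therefore permits either order.

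4. **Would the surgeon know the result?** Yes, once it is reported. Sections 5.1 and 5.2.4 have further surgery depend on final margins and leave re-excision for close margins to the treating surgeon, who is the person surveyed.

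5. **Is there another safeguard?** No section withholds margin status from the surgeon, requires the survey first, or asks for the survey date to be recorded against the date of the pathology report. Late ratings could not be identified afterwards from data the protocol requires.

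6. **How are the other surveys timed?** The calendar footnote ties the radiologist surveys to the procedure, including the day of surgery for lesion localization. Section 5.3 ties the radiation oncologist survey to completion of the initial treatment plan. The surgeon survey is the one that shares an open window with the result most likely to influence it.

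7. **Can the effect be sized?** Let p be the share of surveyed cases with positive margins. Let k_c and k_p be the shares of surveys completed after the report among clear-margin and positive-margin cases. Let d_c and d_p be the changes that knowing the result makes to the proportion of favourable ratings in those late surveys. Then

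   shift in the overall proportion = (1 − p) · k_c · d_c + p · k_p · d_p.

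   The documents give none of these five quantities. If clear margins raise ratings (d_c > 0) and positive margins lower them (d_p < 0), the two terms have opposite signs, and the net shift may be upward, downward or close to zero. If every survey precedes the report (k_c = k_p = 0), the shift is zero. That is the condition the fix aims for.

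**The case against.** The strongest reply is that the text ties the survey to the operation. In Section 5.2.3 the survey sentence comes straight after the specimen is sent and before the histopathology section begins, so the natural reading is soon after surgery. A survey completed after an operation also belongs in a post-operative column, so the calendar does not contradict the text. This stands as a reading of intent. It does not close the gap: in Section 5.1 the same sentence follows the sentences on final pathology and re-excision, and nothing enforces prompt completion.

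A second reply is that a retrospective opinion is a legitimate form of perceived usefulness, and that the protocol promises no outcome-blinded rating. That is fair. The endpoint is exploratory and descriptive, with no test, threshold or decision rule attached. This limits the weight of the point without removing it.

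A reader might go further in three ways that the documents do not support.

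- **That surgeons will rate after seeing the margins.** The calendar gives a window and no order. The documents show only that they may.
- **That Section 8.1.1 confirms late completion.** It says "Surveys from providers will be collected at the completion of a patient's on study procedures". That governs when the study team collects the forms. It covers all providers, including radiologists, whose surveys the calendar footnote has completed at the time of the procedure. Late collection is not evidence of late completion.
- **That the plan will report a spurious association between rated usefulness and margin status.** No cross-tabulation of the two is planned. What is exposed is the overall frequency table.

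**Conclusion.** The point holds as a permission in the plan: a surgeon may complete the survey after learning the margin result, at any time up to six weeks after surgery, without departing from the protocol. This can bias the frequency table for secondary objective 2 by an amount and in a direction that the documents do not allow to be computed. The conclusion rests on two things: the calendar marks as printed, and the inference from Sections 5.1 and 5.2.4 that the treating surgeon sees the margin report. It assumes nothing about how often late completion will happen. The primary correlation analyses and their sample size are untouched. The change is worth making because it is cheap; the point does not threaten the study.

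**What to change.** In the calendar and in Sections 5.1 and 5.2.3, ask for the surgeon survey on the day of surgery, or at the latest before the surgeon receives the final pathology report. Record the date the survey was completed and the date of the pathology report. In Section 9.6, add that surveys completed after the report will be tabulated separately. If prompt completion proves impractical, recording both dates still allows the split table.

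This brings the surgeon survey into line with the procedure-tied timing already used for radiologists. It adds no patient procedure and changes no care. The costs are a prompt to surgeons, tracking of two dates per case, and possibly a late-survey group too small to say much about, since only breast-conserving cases are surveyed.
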